11.3. Data management (data review)

The eForms marked as source data verified by Monitoring are checked for consistency and plausibility by Data Management. Any queries (=discrepancies) are generated via the Internet and are therefore visible to both the investigator and monitor as soon as they are created in the system by means of "marks" (icons). Data Management locks all eForms that it finds to be fully correct, meaning they are protected from further processing. "Marks" indicate this processing status.

The individual working steps carried out by Data Management are specified in SOPs (= standard operating procedures) and WIs (= working instructions).

Justification for the amendment:

- The age limit in the inclusion and exclusion criteria is being raised (reason: there are a number of sprightly patients who will tolerate the study follow-up phase well and can remain compliant. The primary objective of the study will not be affected by a potential increase in the incidence of deaths that are not breast cancer related.)
- Correction of the permitted N-stages of the tumour from N1 to N+ (reason: it is expected that all patients, regardless of their N-stage at the time of diagnosis will benefit from extending the therapy with anastrozole beyond 5 years)
- Addition to the exclusion criterion: "Manifest secondary malignancy or status post secondary malignancy" with the following exceptions: a) simultaneous bilateral breast cancer, oestrogen and/or progesterone receptor-positive on both sides at the time of diagnosis (reason: because of the simultaneity of the tumour occurrence, such a carcinoma is interpreted as a multi-centric carcinoma); b) in-situ carcinoma of the cervix and basal cell carcinoma of the skin, is a correction of the data in the CRF and protocol, as these exceptions were defined in the CRF (reason: the probability of relapse in these carcinomas is minimal.)
- Extension of the recruitment phase for 1 year (reason: the annual recruitment rate was overestimated in the study planning phase.)

- The flow chart will be adjusted following the protocol amendments as per Amendment 1.
- The Data Management System of ABCSG is being changed from the PDF-format based IntTrial® system (CRS – Creative Research Solutions GmbH) to the web-based MACRO® data management system (software from InferMED). This change was prompted by the withdrawal of support for IntTrial® on the part of the system developer.

Initiators of the amendment:

Study sites affected by the amendment

The amendment applies to all participating study sites in this study.

The study protocol shall be amended as follows:

Affected protocol point:

Point 1.1. Study summary/study schedule (protocol, page 11; amendment 2, page 3) and point 4. Design (protocol, page 21; amendment 2, page 3)

Old text:

Planned recruitment end:	December 2009
Planned end of the maximum treatment phase:	December 2014
Planned end of follow-up:	December 2019

Amended text:

Planned recruitment end:	June 2010
Planned end of the maximum treatment phase:	June 2015
Planned end of follow-up:	June 2020

Affected protocol point:

10.6. Substitution of patients (protocol, page 35)

Old text:

No patient who meets the inclusion and exclusion criteria and who stops taking part in the study early for any reason will be replaced.

Amended text:

No patient who meets the inclusion and exclusion criteria and who stops taking part in the study early for any reason will be replaced. **Patients who are found to not meet the inclusion and exclusion criteria at study enrolment during monitoring can be replaced.**

Justification for the amendment:

- Extension of the recruitment phase for 6 months (reason: the annual recruitment rate was overestimated in the study planning phase.)
- Substitution of ineligible patients (reason: the required number of evaluable patients will be guaranteed by substitution.)

Initiators of the amendment:

Coordinating Investigator: [REDACTED]

Statistics: [REDACTED]

Sponsor: AstraZeneca Österreich GmbH, Medical Director: [REDACTED]

Agreement for Protocol Amendment No. 3

Title: A Prospective, Randomised, Open, Multicentre Phase III Study to Assess the Efficacy of Secondary Adjuvant Endocrine Anastrozole Therapy for 2 Further Yrs vs 5 Further Yrs in Patients With HR +ve Breast Cancer After 5-yr Primary Adjuvant Endocrine Therapy

Study no.: 1033AU/0003

Version: Final version dated 27/11/2009

I agree with the contents of this protocol amendment.

.....
Date 

Coordinating Investigator

University Clinic for Surgery

[name]

Agreement for Protocol Amendment No. 3

Title: A Prospective, Randomised, Open, Multicentre Phase III Study to Assess the Efficacy of Secondary Adjuvant Endocrine Anastrozole Therapy for 2 Further Yrs vs 5 Further Yrs in Patients With HR +ve Breast Cancer After 5-yr Primary Adjuvant Endocrine Therapy

Study no.: 1033AU/0003

Version: Final version dated 27/11/2009

I agree with the contents of this protocol amendment.

.....
Date [REDACTED]

[REDACTED],
ABCSG statistician
Austrian Breast and Colorectal Cancer Study Group
[name]
[name]

Agreement for Protocol Amendment No. 3

Title: A Prospective, Randomised, Open, Multicentre Phase III Study to Assess the Efficacy of Secondary Adjuvant Endocrine Anastrozole Therapy for 2 Further Yrs vs 5 Further Yrs in Patients With HR +ve Breast Cancer After 5-yr Primary Adjuvant Endocrine Therapy

Study no.: 1033AU/0003

Version: Final version dated 27/11/2009

I agree with the contents of this protocol amendment.

.....
Date 

Medical Director

SAE	Serious adverse event
SAF	Safety
SAP	Statistical Analysis Plan

## 1. Introduction

The Austrian Breast & Colorectal Cancer Study Group (ABCSCG) is a cooperative institution that was set up to conduct controlled clinical trials in breast and colorectal cancer and to facilitate communication and the dissemination of knowledge among scientists and others dedicated to the cancer problem. Since its establishment in 1984, more than 15,000 patients have been enrolled in ABCSCG investigations. In certain patient risk groups, ABCSCG is currently recruiting up to 40 per cent of all Austrian breast cancer patients to their clinical trials. The ultimate goal of the ABCSCG is to enhance the standard of cancer treatment in this country and abroad by developing innovative approaches and testing increasingly more effective therapeutic strategies.

Prospectively randomized clinical investigations have come to be seen as the only instrument to generate valid and reliable clinical data, to gain insights into significant prognostic and predictive factors, and thus to enhance all aspects of evidence-based medicine. As a target of oncological research and practice, the ABCSCG has selected two of the most common malignancies affecting women and men in the present-day western world: carcinoma of the breast and bowel.

As a whole, the ABCSCG collaborates toward the common goal of controlling, effectively treating, and ultimately curing cancer by means of large, multicenter cancer trials in the (neo-) adjuvant setting. Research results are provided to the medical community through scientific publications and professional meetings.

This Statistical Analysis Plan (SAP) is based on the Amended Clinical Study Protocol for ABCSCG study 16 (1033AU/0003) and gives a detailed description of all statistical analyses planned to be conducted within this trial at predefined time points.

## 2. Study details

ABCSCG-16 is a prospective, randomized, open-label, multicenter Phase III study in endocrine-responsive postmenopausal women with early breast cancer who have already received their standard 5 years of adjuvant endocrine treatment

Patients aged  $\leq 80$  years, who are recurrence-free 60 months after the operation and who have completed a primary 5-year endocrine treatment, are being randomized to receive a further 2 (arm A) or 5 (arm B) years of treatment with anastrozole.

### 2.1. Study design

All patients free of recurrence 60 ( $\pm 12$ ) months after operation are randomized following a primary 5-year endocrine therapy with therapy intervals of maximal 12 months (e.g. from studies 8 and 9) as follows:

- Arm A: 2-year anastrozole therapy (Arimidex®)
- Arm B: 5-year anastrozole therapy (Arimidex®)

### 2.1.1. Study duration

The duration of therapy is 2 or 5 years respectively. The follow-up period will last 8 years for arm A and 5 years for arm B.

Scheduled study start: December 2003

Scheduled end of recruitment: original protocol: December 2008  
protocol amendment 3: June 2010

#### 2.1.1.1. *End of treatment*

Scheduled end of max. treatment phase: original protocol: December 2013  
protocol amendment 3: December 2015

#### 2.1.1.2. *End of study*

Scheduled end of follow-up: original protocol: December 2018  
protocol amendment 3: December 2020

## 2.2. **Study objectives**

### 2.2.1. Primary objective

The primary objective is the assessment of the effect of 2 further years of anastrozole treatment vs. further 5 years of anastrozole treatment on disease-free survival (DFS), following a five-year adjuvant endocrine therapy.

### 2.2.2. Secondary objectives

- Assessment of the effect of further 2 years of anastrozole treatment vs. 5 further years of anastrozole treatment on the overall survival (OS) following five years of adjuvant endocrine therapy.
- Comparison of the respective rates of fracture occurrence in the two groups
- Comparison of the occurrence of secondary carcinoma in the two groups
  - Comparison of the occurrence of contra-lateral breast cancer in the two groups, respectively
  - Comparison of the occurrence of secondary carcinoma except the contra-lateral mammary carcinoma in the two groups respectively

## 2.3. Randomization and stratification criteria

Stratification criteria:

The following stratification criteria are applied:

- 1) pT-Stadium:
  - i) - pT1( $\leq 2$  cm)
  - ii) - pT2 ( $> 2 - 5$  cm)
  - iii) - pT3( $> 5 - 10$  cm)
  
- 2) pN-Stadium:
  - i) no lymph node metastasis
  - ii) 1 - 3 lymph node metastasis
  - iii) 4 - 9 lymph node metastasis
  - iv)  $\geq 10$  lymph node metastasis
  
- 3) Adjuvant primary hormone therapy :
  - i) 5 years of anti-estrogen
  - ii) 2 years of anti-estrogen + 3 years anastrozole
  - iii) Another, comparable endocrine therapy
  
- 4) Adjuvant chemotherapy :-
  - i) Chemotherapy containing anthracycline
  - ii) Chemotherapy containing taxane
  - iii) Other chemotherapy
  - iv) No chemotherapy
  
- 5) Participation in a clinical study:
  - i) Study 8 (ABCSCG)
  - ii) Study 9 (ABCSCG)
  - iii) None
  
- 6) Receptor status:
  - i) ER+PgR+
  - ii) ER+PgR-
  - iii) ER-PgR+
  
- 7) Federal states:
  - (I) Vienna
  - (II) Lower Austria
  - (III) Burgenland
  - (IV) Styria
  - (V) Carinthia
  - (VI) Upper Austria
  - (VII) Salzburg
  - (VIII) Tyrol
  - (IX) Vorarlberg

## 2.4. Number of subjects - sample size estimation

As of randomization, all patients receive the same therapy for 2 years. After that, one group will continue the therapy for 3 further years. Therefore, differences between the groups are only to be expected 2 years after randomization. Therefore, the most relevant point in time regarding evaluation of the data will be 2 years after randomization (i.e. change of therapy) for each patient.

It is to be expected that 700 patients can be recruited per year. Considering that 5% of patients will drop out of the study within the first 2 years due to recurrence, an effective rate of recruitment of 665 remains.

A difference between the therapy group and the control group of 0.916 and 0.937 3 years after change of therapy at exponential survival (corresponding to a hazard quotient of 1.35) can be uncovered with 85% power at a two-sided level of significance of 5%, if 433 events are observed. This is feasible, if 665 patients are recruited annually for 5 years and followed up for another 2.7 years, amounting to a case number of 3,500, and of these 3325 evaluable patients. The expected total duration of the study is 9.7 years.

With an exponential drop-out rate of 7%, the power would be reduced to 80%.

## 3. Statistical methods

### 3.1. Data handling conventions

#### 3.1.1. Data entry errors and potential outliers

Patients may have potential outliers for particular observations. Observations will be checked for correctness by the study team before data freeze and at the time point of data freeze all data should be correct. Remaining potential outliers based on correct values will be included in analysis. Values found to be incorrect due to data entry error after data freeze will be excluded from all analyses as missing values.

#### 3.1.2. Missing data

Subjects may have missing specific data points for a variety of causes. In general, data may be missing due to a missed visit, non-evaluability of a specific clinical measurement at its planned clinical visit or a subject's early withdrawal from study. The general procedures outlined below describe what will be done when a data point is missing.

##### 3.1.2.1. *Imputations of missing data*

Generally, only evaluable measurements are considered for the analyses. No values are imputed for missed or non-evaluable visits. In case of primary and secondary efficacy endpoints possible specific requirements are stated in the according analysis sections.

### 3.1.2.2. Partial dates

Partially incomplete dates (day or day/month missing) will be imputed for dates of progression as well as for therapy begin and/or end dates. Completely missing dates and missing years will not be imputed.

#### Imputation Rules for Partial Progression Dates

	Missing	Impute	Exception
Oncological Event Date	Day	01	Default to the Randomization date if the imputed date is before the Randomization date.
	Day /Month	01JAN	
Death Date	Day	01	Default to the Randomization date if the imputed date is before the Randomization date.
	Day /Month	01JAN	
Fracture Date	Day	01	Default to the Randomization date if the imputed date is before the Randomization date.
	Day /Month	01JAN	

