## 3.3. Definition of populations for analyses

### 3.3.1. Per-protocol (PP) population

Primary endpoint analysis will be based on the PP; that is, all patients who were randomized, signed the Informed Consent, comply with inclusion and exclusion criteria and have had at least one follow-up examination after randomization and who survived without recurrence for two years. All subjects will be analyzed according to the therapy arm to which they have been

randomized. Subjects who terminate the study before their scheduled final study visits will be censored.

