#### *Types of analyses for the primary endpoint*

##### Main analysis:

Start time for DFS: 2 year after randomization

Population: PP

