#### *Evaluation of censoring date for DFS analysis*

In case of no events and no early study termination, patients will be censored after 10.5 years. The last DFS event free day is evaluated as the maximum of the last treatment visit date and last follow up visit date including only visits with cancer status evaluation. In case of follow-up visits with documented cancer status but without a documented visit date, the lower bound of the due visit date window will be used. Follow-up visits with information whether patient is alive but without cancer status evaluation will not be used.

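### Partial event dates are imputed to the earliest possible day with randomisation as the only floor, so an event can precede a documented event-free visit or the 2-year start, and the SAP does not say how the latter is handled

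*SAP*

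**What the plan says.** SAP 3.1.2.2 states that "Partially incomplete dates (day or day/month missing) will be imputed for dates of progression as well as for therapy begin and/or end dates". Its table for event dates begins "Oncological Event Date Day 01"; when the month is also missing, the date becomes 1 January. Death and fracture dates follow the same rule. The one exception for all three is "Default to the Randomization date if the imputed date is before the Randomization date".

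SAP 3.1.2.1 says that for efficacy endpoints "possible specific requirements are stated in the according analysis sections". Sections 3.5 and 3.6 add no lower bound on an event date. Under the censoring rules in 3.5.2, "The last DFS event free day is evaluated as the maximum of the last treatment visit date and last follow up visit date", counting only visits with a cancer status evaluation. Those visits set the censoring date and are not used to bound an event date.

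The main DFS analysis has "Start time for DFS: 2 year after randomization" and uses the per-protocol population, which under 3.3.1 is limited to patients "who survived without recurrence for two years". Sensitivity analysis 1 and the main analyses of OS, contralateral breast cancer and second cancer also start at 2 years. Sensitivity analysis 2 and the sensitivity analyses of those three secondary endpoints start at randomisation. Time to first fracture (3.6.4) is defined only from 2 years.

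**The concern.** The earliest possible day is a defensible convention only if it is bounded by what is already known about the patient. Here three kinds of contradiction are possible.

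- **Event before a clean visit.** A patient is documented disease-free in June and relapses later that year. If only the year is recorded, the relapse is dated 1 January.
- **Death before relapse or last contact.** A relapse is fully dated in May and the death is known only by the same year, so the death is dated 1 January. DFS takes the earliest event, so the imputed death replaces the correctly dated relapse.
- **Event before time zero.** A patient passes the 2-year point in March and has an event in October of that year, recorded by year only. It is dated 1 January, before the clock starts. Because the rule always moves dates earlier, it can carry events out of the post-2-year window but never into it.

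At stake is whether a few real events have a valid, reproducible place in the main analyses.

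**Working it through.** **Yardstick.** SAP 2.4 plans on 433 events, HR 1.35, two-sided 5% and 85% power. The usual formula gives D = 4(1.960 + 1.036)² / (ln 1.35)² = 35.9 / 0.0901 ≈ 399, so 433 is not reproduced. With 433 events, power is Φ(√433 × 0.3001/2 − 1.960) = Φ(1.162) = 87.7%. That mismatch is a separate matter; 433 serves here only as a scale.

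**Size of the shift.** For a date spread evenly over its possible range, the mean shift is about 15 days (day missing) or about 183 days (day and month missing), always earlier.

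**Worked example.** Randomised 15 March 2006, so the 2-year start is 15 March 2008. Disease-free visit on 10 March 2008. Relapse recorded as 2008. The rule gives 1 January 2008, before both the clean visit and the start.

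**Share dated before the last event-free visit.** Assume annual visits on the anniversary and event dates independent of visits. A year-only date precedes the last visit when the anniversary falls earlier in the calendar year than the event, which has probability about 1/2. For a missing day it is about 1/24 = 4%. Simulation gave about 52% and 4% with visits on the anniversary, and 46% and 4% with visits spread over the full ±6 months that the protocol allows.

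**Share of post-landmark events dated before the 2-year start.** Assume a constant hazard at the average of the two design hazards and 2-year points spread evenly over the calendar year.

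- Hazards: −ln(0.916)/3 = 0.0292 and −ln(0.937)/3 = 0.0217; average λ = 0.0255.
- Probability of an event between the start and the end of that calendar year: 1 − (1 − e^−λ)/λ = 0.0126.
- Follow-up after the start: the SAP states that "In case of no events and no early study termination, patients will be censored after 10.5 years", so 10.5 − 2 = 8.5 years; 5.7 years is taken as a shorter assumption.
- Probability of an event over follow-up: 1 − e^(−8.5λ) = 0.195, or 1 − e^(−5.7λ) = 0.135.
- Share for year-only dates: 0.0126/0.195 = 6.5%, or 0.0126/0.135 = 9.3%. Simulation agrees.
- Share for day-missing dates: (λ/24)/0.195 = 0.5%, or (λ/24)/0.135 = 0.8%.

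**Events affected**, if a share q of 433 events is year-only (q is assumed):

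| q | 433 × q × 0.065 | 433 × q × 0.093 |
|---|---|---|
| 1% | 0.3 | 0.4 |
| 5% | 1.4 | 2.0 |
| 10% | 2.8 | 4.0 |
| 20% | 5.6 | 8.1 |

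If all 8.1 were excluded, power would be Φ(√424.9 × 0.3001/2 − 1.960) = 87.1%, against 87.7%. Day-missing dates affect less than one event even at q = 20% (433 × 0.20 × 0.008 = 0.7).

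**Fracture.** The window runs from 2 to about 5 years. With fractures spread evenly over it, about 0.5/3 = 17% of year-only fractures would be dated before the start.

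**Is a visit floor enough?** In the example it gives 11 March 2008, still before 15 March. In simulation it removes the problem if visits fall exactly on anniversaries. With visits spread over ±6 months it leaves 4.5% to 6.4% of year-only events before the start, so a landmark rule is needed too.

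**The case against.** The case that this is housekeeping is strong.

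- **Few dates should be partial.** Protocol 8.1 asks for the exact verification date of locoregional relapse and distant metastasis. The data management section revised by Amendment 2 provides edit checks, tracked queries and a plausibility review, and SAP 3.1.1 has data checked before freeze. This stands, with a limit: 8.1 makes no such request for deaths, second cancers or fractures. Protocol 7.3 lets survival status come from the registration office or the GP, and the SAP evidently expects some partial dates, since it writes rules for them.
- **No bias between arms is shown.** A reader might infer that dates which always err early distort the treatment comparison. The documents do not support this: the rule is identical in both arms, and since Amendment 1 the visit schedule is too.
- **Loss of events is not a stated rule.** A reader might infer that every year-only event in the landmark year is removed from the primary analysis. The SAP does not say so. Section 3.3.1 does not state whether 2-year status is judged on the imputed date or on the visit record. What can be said is that handling is unspecified; on either reading the event has no positive time under the imputed date.
- **Other analyses keep the events.** Those from randomisation do, for DFS, OS, contralateral and second cancer, although with too early a date. Fracture has no such analysis.

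**Conclusion.** The point holds as a minor gap. The imputation rule can contradict dates already in the database, and it can place a true post-landmark event before time zero with no instruction on what follows. It does not threaten the trial's conclusion: about 0.3 to 8 of 433 events are affected if an assumed 1% to 20% are year-only, and power changes by at most about 0.6 percentage points (87.7% to 87.1%). These figures rest on a constant hazard, event dates independent of visits, and an assumed share of partial dates that the documents do not give. The ordering contradictions follow from the text alone. The reason to act is that the correction is cheap and removes a choice that would otherwise be made at programming.

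**What to change.** Change the exception column of the event-date table in SAP 3.1.2.2 so that the floor is the latest of:

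- the randomisation date;
- for relapse, second cancer and fracture, the day after the last visit with documented event-free status;
- for death, the last date known alive or the recorded relapse date.

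Add a landmark rule. Where the remaining possible range still straddles the 2-year start, impute the midpoint of that range and use the same date for per-protocol membership and for event time. In the example the range is 11 March to 31 December 2008 (days 71 to 366 of that year). The midpoint is day 218.5, about 5 August, which is after the start.

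Report the number of imputed event dates by arm and by endpoint. The dates needed are already collected, so the cost is a revised table column, a short rule and a small amount of extra programming.
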